9.2.4 Sample Size Determination

The proposed study is a dose escalation (Phase 1) study with an expansion cohort reaching into dose expansion (Phase 2). No formal sample size calculation was performed for dose escalation (Phase 1) of the study. A maximum of 18 patients are planned for dose escalation.

No formal sample size calculation was performed for dose expansion (Phase 2). However, a planned sample size of 52 patients is deemed sufficient to obtain an initial estimate of response rates to formally power a subsequent Phase 2/3 study.

For each indication (ie, breast, gastric, or GEJ cancer), an interim evaluation of efficacy will be conducted when approximately 50% of patients complete Cycle 1 at the recommended dose for expansion based on objective responses determined from RECIST 1.1 or RANO-BM. One analysis will be performed for patients with breast cancer, and another analysis will be performed for patients with gastric or GEJ cancer. If the ORR is <10% for a specific indication (ie, breast or gastric/GEJ), the study will be terminated for that particular indication.

The Statistical Analysis Plan will provide more details on the exact statistical approach.

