 - Dose 1 and Safety Follow-Up Period: Week 0 to Week 3
 - Dose 2 and Safety Follow-Up Period: Week 4 to Week 11 (EOT Visit or Cycle 2 eligibility assessment)
 - Cycle 2 (to begin 2 weeks after the Cycle 2 eligibility assessment for patients with CB during Cycle 1, as long as the cumulative kidney dose remains <23 Gy [based on the dosimetry results during Cycle 1 of dose escalation])
 - Dose 1 and Safety Follow-Up Period: Week 0 to Week 3
 - Dose 2 and Safety Follow-Up Period: Week 4 to Week 11 (EOT Visit)
 - Long-term follow-up period

One treatment cycle is defined as the timeframe of approximately 12 weeks (84 days) that includes 2 administrations of the study drug given 4 weeks apart (including the 4-week Safety Follow-Up Period after Dose 1 and the Safety Follow-Up Period after Dose 2, up to Visit 11).

However, if a patient misses a dose of study drug due to study drug production problems or due to other circumstances (in certain cases), the interval between doses may be extended up to 6 weeks (Cycles 1 and 2 of both dose escalation and dose expansion phases) or up to 12 weeks (Cycles 3 and 4 of the dose escalation phase) (see [Missed Doses](#)).

Dose Escalation Phase

Screening

Patients will be screened for study eligibility over 2 different study visits (Visit 1 and Visit 2) in the 29 days prior to dosing (ie, Day -28 to Day 0 of Cycle 1). Visit 2 should occur preferably within the 14 days prior to study drug administration (Visit 3). All patients will undergo pre-treatment imaging for eligibility and baseline at Visit 1 with a diagnostic CT scan for RECIST version 1.1. Patients with known brain metastases will undergo a brain MRI scan, in addition to the diagnostic CT, for RANO-BM.

After screening, approximately 15 patients who meet inclusion and exclusion criteria will be enrolled into 1 of 4 cohorts, including a minimum of 3 patients each.

The screening period may be extended up to an additional 2 weeks upon Sponsor approval in certain exceptional cases (eg, to allow for a repeat blood draw or to assess previously unavailable imaging results) following a discussion between the Principal Investigator, Medical Monitor, and Sponsor.

CAM-H2 administration

In the dose escalation phase, all patients will receive at least 1 cycle of CAM-H2. Patients with CB may receive up to 4 cycles of CAM-H2, as long as the cumulative kidney dose remains <23 Gy (based on the dosimetry results during Cycle 1). Cycles will be given as 2 IV administrations,

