Staggered dosing will be applied for all cohorts during dose escalation. The first dose of the first patient of each cohort will be administered at least 2 weeks before the first dose of the next 2 patients (sentinel dosing). Once the MTD or RDP2 has been established, 3 additional patients will be enrolled to receive the MTD or RDP2. The patients treated at the MTD or RDP2 in the dose escalation phase will be included in the readout for efficacy. The dose escalation will be done via increases of the nominal activity of CAM-H2 in cohorts of 3 to 6 patients until approximately 15 (or a maximum of 18) patients have been dosed. The actual dose levels administered to the patient can have a tolerance window of ±10% of the prescribed nominal activity.

Dose escalation will be decided based on a review of all the available safety data obtained after completion of Cycle 1 (ie, after 2 IV administrations) of each dose level. If a patient is not able to complete a full cycle due to adverse events (AEs) related to study drug administration, he/she will not be replaced, and the dose escalation rules will be followed.

In the instance that a patient is not able to complete a full cycle due to AEs not related to study drug administration or due to a negative PD distribution scan, he/she will be replaced to ensure safety data spanning a full treatment cycle can be considered for dose escalation.

Imaging

All imaging will be sent to the central imaging core laboratory for independent review as soon as possible within 48 hours of acquisition. Further instructions will be provided by the imaging core laboratory in separate guidelines.

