Staggered dosing will be applied for all cohorts during dose escalation. The first dose of the first patient of each cohort will be administered at least 2 weeks before the first dose of the next 2 patients (sentinel dosing). Once the MTD or RDP2 has been established, 3 additional patients will be enrolled to receive the MTD or RDP2. The patients treated at the MTD or RDP2 in the dose escalation phase will be included in the readout for efficacy. The dose escalation will be done via increases of the nominal activity of CAM-H2 in cohorts of 3 to 6 patients until approximately 15 (or a maximum of 18) patients have been dosed. The actual dose levels administered to the patient can have a tolerance window of $\pm 10\%$ of the prescribed nominal activity.

Dose escalation will be decided based on a review of all the available safety data obtained after completion of Cycle 1 (ie, after 2 IV administrations) of each dose level. If a patient is not able to complete a full cycle due to AEs related to study drug administration, he/she will not be replaced, and the dose escalation rules will be followed.

In the instance that a patient is not able to complete a full cycle due to AEs not related to study drug administration or due to a negative PD distribution scan, he/she will be replaced to ensure safety data spanning a full treatment cycle can be considered for dose escalation.

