Diagnostic CT scans to evaluate disease status	
At screening and after Dose 2 only [3]:
 
 • 4 weeks after CAM-H2 at Visit 10 (Week 8); and • Every 8 weeks after Visit 10 (Week 8), as long as the patient had clinical benefit after Cycle 1 [4] and there is no disease progression. 	
After Dose 2 only [3]:
 
 • 4 weeks after CAM-H2 at Week 8; and • Every 8 weeks after Week 8, as long as the patient had clinical benefit after the current cycle [4] and there is no disease progression.
Brain MRI scans to evaluate disease status [5]	
At screening and after Dose 2 only [3]:
 
 • 4 weeks after CAM-H2 at Visit 10 (Week 8); and • Every 8 weeks after Visit 10 (Week 8), as long as the patient had clinical benefit after Cycle 1 [4] and there is no disease progression. 	
After Dose 2 only [3]:
 
 • 4 weeks after CAM-H2 at Week 8; and • Every 8 weeks after Week 8, as long as the patient had clinical benefit after the current cycle [4] and there is no disease progression.

 1. Patients with a negative PD distribution scan will not be treated further, although they will be included in the SAF. An extra patient will then be included in the same cohort as substitute. 2. During Dose 1 of the cycle, the first planar WB scan will also serve as the PD distribution scan. 3. Imaging to evaluate disease status after treatment will start 4 weeks after the last CAM-H2 infusion (Dose 2) of the cycle at Week 8. If a patient cannot receive Dose 2 of a given cycle, his/her imaging to evaluate disease status will start at the theoretical timing for Dose 2 (ie, 4 weeks after Dose 1 of the cycle). 4. Patients without clinical benefit after the current cycle will have another diagnostic CT scan and brain MRI (if indicated) at Week 11, which will be EOT. 5. Brain MRI will only be performed in patients with known brain metastases. 		

CT = computed tomography; EOT = End of Treatment; MRI = magnetic resonance imaging; NA = not applicable; PD = pharmacodynamic(s); SAF = Safety Analysis Set; SPECT = single photon emission computed tomography; WB = whole body.
		

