3.1.4.2 Dose escalation rules

DLTs will determine the progression/escalation with the following rules:

- If 0 out of 3 patients experience a DLT, all patients will proceed to the next higher dose level;
- If 1 out of 3 patients experiences a DLT, the same dose will be given to 3 new patients:
 - If 0 of the 3 new patients experience a DLT, all patients will proceed to the next higher dose level; and/or
 - If 1 or more of the 3 new patients experiences a DLT (≥ 2 of the 6 patients) this dose will become the MTD + 1.
- If ≥ 2 out of 3 patients experience a DLT, the MTD has been exceeded and a lower dose should be tested between this dose and the previous dose level;
- Once the MTD + 1 has been established, 3 additional patients will be exposed to the dose below the MTD + 1; and
- If the MTD + 1 is not reached, 3 additional patients will be exposed to the highest dose.

Within the planned dose range, a dose lower than the next planned dose may also be tested, depending on emerging safety, tolerability, and/or other relevant data, such as dosimetry or PD. If the highest planned dose level is found to be safe and tolerable, also considering the PD data, additional higher doses may be added by amendment.

A period of at least 4 weeks will be maintained between 2 consecutive cohorts.

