4.3 Withdrawal Criteria

Participation of a patient in this clinical study may be discontinued for any of the following reasons:

- Withdrawal of consent or a request to discontinue from the study for any reason;
- Occurrence of any medical condition or circumstance that exposes the patient to substantial risk and/or does not allow the patient to adhere to the requirements of the protocol;
- Occurrence of any SAE, clinically significant AE, severe laboratory abnormality, intercurrent illness, or other medical condition which indicates to the Investigator that continued participation is not in the best interest of the patient;
- Pregnancy;
- Requirement of prohibited concomitant medication;
- Patient failure to comply with protocol requirements or study-related procedures; or
- Termination of the study by the Sponsor or the regulatory authority.

If a patient withdraws prematurely from the study due to the above criteria or any other reason, study staff should make every effort to complete the full panel of assessments scheduled for the EOT Visit (Visit 11 in Cycle 1 or Visit 20 in Cycle 2 of either the dose escalation or dose expansion phases). The reason for patient withdrawal must be documented in the electronic case report form (eCRF).

In the case of patients lost to follow-up, a minimum of 3 attempts to contact the patient (ie, 2 phone calls and 1 certified letter) must be made and documented in the patient's eCRF.

Withdrawn patients may be replaced to ensure adequate numbers of evaluable patients at the discretion of the Sponsor with agreement from the Investigator.

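### The stated maximum of 18 patients in dose escalation is not one that the 3+3 rules over four planned levels keep to: two expanded levels can need 21, before replacements

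*Combined protocol and SAP*

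**What the plan says.** The limit stands in four places: Section 9.2.4 ("A maximum of 18 patients are planned for dose escalation"), Section 3.1.1.2, where dosing proceeds "in cohorts of 3 to 6 patients until approximately 15 (or a maximum of 18) patients have been dosed", and the two matching parts of the Synopsis. Section 3.1.1.1 and the Synopsis give the expected size: "approximately 15 patients who meet inclusion and exclusion criteria will be enrolled into 1 of 4 cohorts", with at least 3 in each. Table 3 in Section 5.1 lists the four levels and marks Level 4 as optional.

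Other provisions determine how many patients are needed:

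- **Expansion of a level (Section 3.1.4.2).** "If 1 out of 3 patients experiences a DLT, the same dose will be given to 3 new patients". Nothing limits how many levels may be expanded in this way.
- **Final 3 patients (Sections 3.1.1.2 and 3.1.4.2).** Three further patients go to the level below MTD + 1 or, if MTD + 1 is not reached, to the highest level. Both sections word this as something that will happen.
- **Intermediate doses (Section 3.1.4.2).** These are tested after 2 or more DLTs in 3 patients, and may also be tested on emerging data.
- **Replacements.** For a patient who cannot complete the cycle because of an unrelated adverse event or a negative distribution scan, Section 3.1.1.2 says "he/she will be replaced to ensure safety data spanning a full treatment cycle can be considered for dose escalation". Footnote 1 of Table 1 (Section 3.1.1.3) says of scan-negative patients "An extra patient will then be included in the same cohort as substitute". Section 4.3 adds "Withdrawn patients may be replaced to ensure adequate numbers of evaluable patients at the discretion of the Sponsor".

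**The concern.** A maximum is a bound. The rules that generate the patient count should either respect it or say what happens when they collide with it. Here 18 equals the count when one of four levels is expanded, and the text neither limits expansion to one level nor says which provision gives way.

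At stake are the stated size of the escalation phase and, less often, its main output. Section 2.1 makes determination of the MTD and the recommended Phase 2 dose part of the primary objective of escalation. If dosing stops at 18, the final 3 patients may not be enrolled and, on a few paths, the MTD decision is not reached.

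**Working it through.** **Inputs.** Four levels (Sections 3.1.1.1 and 5.1). 3 patients per level, 6 if 1 of the first 3 has a DLT; escalation after 0/3 or 1/6; stop after 2 or more DLTs; final 3 patients (all Section 3.1.4.2). The documents give no DLT or replacement rates, so those below are assumptions.

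**Two readings of the final 3.** *Always added*: 3 more patients in every case. *Fill to 6*: 3 more only if the chosen level has 3. The text supports either: Section 3.1.4.2 calls for 3 more patients, while Section 3.1.1.2 speaks of cohorts of 3 to 6.

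**The plan's own figures.** About 15: 4 × 3 + 3 = 15. Maximum 18: 4 × 3 + 3 + 3 = 18, which is one level expanded, all four cleared and the final 3 added.

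**Totals when all four levels are used and cleared.**

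| Levels expanded | Always added | Fill to 6 |
|---|---|---|
| 0 | 15 | 15 |
| 1 | 18 | 15 or 18 |
| 2 | 21 | 18 or 21 |
| 3 | 24 | 21 or 24 |
| 4 | 27 | 24 |

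Under fill to 6 the lower figure applies when Level 4 is one of the expanded levels. With Levels 1 and 2 expanded, both readings give 6 + 6 + 3 + 3 + 3 = 21. Paths that stop early can need fewer: if Level 2 is expanded and stops escalation, the total is 3 + 6 + 3 = 12.

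**Probabilities.** I enumerated every path exactly, with no intermediate level and no replacements; if Level 1 itself exceeds the MTD, no final 3 are added. For a DLT rate p, a level clears with 3 patients with probability (1 − p)³ and clears with 6 with probability 3p(1 − p)² × (1 − p)³. For p = 0.05 these are 0.8574 and 0.1161. The chance that all four levels clear with exactly two expanded is 6 × 0.8574² × 0.1161² = 0.059. Adding the remaining paths above 18 gives 7.1%.

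| Assumed DLT rates, Levels 1 to 4 | >18, always added | >18, fill to 6 | Exactly 21, always added | >18 before MTD decision |
|---|---|---|---|---|
| 5% flat | 7.1% | 3.9% | 6.5% | 0.6% |
| 5/10/15/20% | 17.0% | 8.6% | 14.3% | 2.7% |
| 10% flat | 14.5% | 8.5% | 12.3% | 2.2% |
| 10/15/20/30% | 17.8% | 10.2% | 14.1% | 3.7% |

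The mean need is 14.7 to 16.4 patients across these sets and both readings. At a flat 30% escalation usually stops early, and the chance of exceeding 18 is 5.7% (fill to 6: 3.4%).

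**Three levels only.** Always added: the maximum is 3 × 6 + 3 = 21, and 18 is exceeded in 0.2 to 1.4% of runs under the first three rates of each set. Fill to 6: the maximum is 3 × 6 = 18, never exceeded.

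**Replacements.** Section 3.1.1.2 counts patients dosed, and the distribution scan follows dosing, so a scan-negative patient and the substitute both count. Runs needing exactly 18 make up 27.4 to 34.5% of the total (fill to 6: 26.6 to 32.0%), and one replacement takes any of them past 18. If each dosed patient were independently replaced with probability 2%, 18 would be exceeded in 17 to 28% of runs (fill to 6: 12 to 18%). At 5% the figures are 26 to 38% and 21 to 28%. Both rates are illustrations only.

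**The case against.** The strongest reply is that 18 is a cap, not a forecast: Section 3.1.1.2 has dosing run until that number is reached, so what is missing is a sentence on what follows, not consistency. The sponsor also has means of staying within it. Level 4 is optional, the sponsor confirms each escalation (Section 3.1.4), the Safety Review Committee decides on continued dosing (Section 3.1.5.1), and replacement under Section 4.3 is discretionary. Expansion may follow determination of either the MTD or the recommended dose (Section 3.1.2.1), and no inference depends on 18, since Section 9.2.4 says no formal calculation was made.

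Much of this stands. The wording does imply a stop at 18, the consequence is small, and three levels with fill to 6, no intermediate level and no replacements stay within 18. The cap reading does not remove the conflict, however. Sections 3.1.1.2 and 3.1.4.2 require the final 3 patients, and Section 3.1.1.2 requires certain replacements, so a path that needs 21 cannot satisfy both the rules and the cap. Discretion makes such paths rarer but does not say which provision prevails. The Safety Review Committee charter might, but it is not among the documents.

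A reader might infer that escalation will probably exceed 18, or that two expanded levels always need 21. Neither follows. Two expanded levels can end at 18 or fewer, and the larger percentages above rest on replacement rates that the documents do not give.

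**Conclusion.** The point holds as an inconsistency of modest size. Over four planned levels the rules can require 21 patients on either reading of the final 3, and up to 27 (24 with fill to 6), against a stated maximum of 18. Under the four assumed sets of DLT rates, without replacements or intermediate doses, the chance of needing more than 18 is about 7 to 18%, or 4 to 10% with fill to 6. Replacements raise it by an amount the documents do not allow one to estimate.

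Most overshoots are to exactly 21 and concern only the final 3 patients. The expansion phase can make these up, because Section 3.1.2.1 sets a total of at least 52 at the chosen dose. More than 18 before the MTD decision is uncommon, at about 0.6 to 4% on the same assumptions. It would therefore be wrong to read this as showing that the design is invalid or that the MTD cannot be determined; the documents do not support that.

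**What to change.** Reconcile the wording in Sections 3.1.1.2 and 9.2.4 and the two matching Synopsis passages, leaving every dose and escalation rule as it is. Either of two changes would do.

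- **(a) Restate 18 as a planning figure.** Suggested text: *Approximately 15 to 18 patients are expected. If more than one level is expanded, the rules of Section 3.1.4.2 may require 21 or more (up to 27 over four levels), plus any replacements and intermediate dose levels.*
- **(b) Keep 18 as a cap and state its consequence.** Suggested text: *No more than 18 patients will be dosed in escalation, and all dosed patients, including those later replaced, count towards this number. If 18 is reached first, the 3 additional patients, and in a few cases the MTD decision, may not be reached.*

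In either case, say whether the 3 additional patients are added to a level that already has 6. If they are not, the upper figure in (a) becomes 24. Section 3.1.1.1 and its Synopsis counterpart give only the approximate 15 and need no change.

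The cost is a text change in four places. Option (a) makes the stated size less definite. Option (b) keeps it definite but puts on record that escalation may end incomplete.

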10 DATA MANAGEMENT AND RECORD KEEPING

10.1 Data Management

10.1.1 Data Handling

Data will be recorded at the site on eCRFs and reviewed by the clinical research associate (CRA) during monitoring visits. The CRAs will verify data recorded in the EDC system with source documents. All corrections or changes made to any study data must be appropriately tracked in an audit trail in the EDC system. An eCRF will be considered complete when all missing, incorrect, and/or inconsistent data have been accounted for.

10.1.2 Computer Systems

Data will be processed using a validated computer system conforming to regulatory requirements.

10.1.3 Data Entry

Data must be recorded using the EDC system as the study is in progress. All site personnel must log into the system using their secure user name and password in order to enter, review, or correct study data. These procedures must comply with Title 21 of the Code of Federal Regulations (21 CFR Part 11) and other appropriate international regulations. All passwords will be strictly confidential.

10.1.4 Medical Information Coding

For medical information, the following thesauri will be used:

- Medical Dictionary for Regulatory Activities (most current version) for medical history and AEs; and
- WHO Drug Dictionary for prior and concomitant medications.

10.1.5 Data Validation

Validation checks programmed within the EDC system, as well as supplemental validation performed via review of the downloaded data, will be applied to the data in order to ensure accurate, consistent, and reliable data. Data identified as erroneous, or data that are missing, will be referred to the site for resolution through data queries.

The eCRFs must be reviewed and electronically signed by the Investigator.

10.2 Record Keeping

Records of patients, source documents, monitoring visit logs, eCRFs, inventory of study drug, regulatory documents, and other Sponsor correspondence pertaining to the study must be kept in the appropriate study files at the site. Source data are defined as all information in original records and certified copies of original records of clinical findings, observations, or other activities in a clinical study necessary for the evaluation and reconstruction of the clinical study. Source data are contained in source documents (original records or certified copies). These records will be retained in a secure file for the period as set forth in the Clinical Study Agreement. Prior to transfer or

destruction of these records, the Sponsor must be notified in writing and be given the opportunity to further store such records.

10.3 Study End

The study end is defined as 12 months after the last patient's EOT/ET Visit.

11 INVESTIGATOR REQUIREMENTS AND QUALITY CONTROL

11.1 Ethical Conduct of the Study

Good Clinical Practice (GCP) is an international ethical and scientific quality standard for designing, conducting, recording, and reporting studies that involve human patients. Compliance with this standard provides public assurance that the rights, safety, and wellbeing of study patients are protected, consistent with the principles that have their origin in the Declaration of Helsinki, and that the clinical study data are credible.

